PROTOCOL

Pilot Clinical Trial on the Effects of Dietary Fibres on Gut Microbiome and Metabolic Profiles in a Transgenerational Cohort

Table of Contents

- 1. Introduction
- 2. Study Hypothesis
- 3. Study Aim
- 4. Primary Outcome
- 5. Secondary Outcomes
- 6. Study Methodology
- 7. Intervention Products
- 8. Study Design
- 8.1 Participants' Recruitment
- 9. Study Design
- **10. Statistical Analysis**
- 11. Withdrawal Criteria and Adverse Events
- 12. Regulatory Issues
- **13. Publication Policy**
- 14. References

1. Introduction:

Westernised diets, rich in animal proteins and fats and low in dietary fibres, have become more common around the world in the past 3-4 decades¹. This trend has been accompanied by a rise in cardiometabolic conditions (diabetes, obesity, heart disease) as well as allergies. However, no causal relationship between these trends has been proven yet. Dietary fibres are complex plant polysaccharides which reach the colon intact; there they are broken down into smaller molecules, such as short-chain fatty acids by the gut bacteria². Examples of short-chain fatty acids include acetate, propionate or butyrate. These molecules end up in the blood stream where they perform a wide range of significant functions, such as appetite regulation, control of colon cells development etc^{2,3}. Increased intake of dietary fibres which leads to a diverse gut bacteria composition and consequently increased production of short-chain fatty acids is associated with good health². Examples of health benefits include lower risks of heart disease or type 2 diabetes.

The recommended daily intake of dietary fibre is 30g, nonetheless, the average daily intake is around 15-18g^{4,5}. A trend characterised by decreased dietary fibre intake has become more apparent in the past decades in various countries around the world^{5,6}. Younger people tended to consume fewer dietary fibres when compared to older people^{5,6}. Among younger people, dietary fibres were generally replaced with animal fats and proteins.

A human study indicated that migration from non-Westernised societies (Thailand), where intake of dietary fibres is high, to Westernised societies (USA), where intake of dietary fibre is low, leads to loss of gut bacteria diversity⁷. This loss was associated with increased BMI (body mass index) and these negative effects exacerbated the longer the individuals spent in the USA. Indeed, second generation migrants had lower gut bacteria diversity, higher protein intake and higher BMI when compared to first generation migrants or individuals who remained in Thailand⁷. In addition, a mice study demonstrated that breeding mice on low fibre diets over 4 generations led to 70% of gut bacteria taxa (population) being lost in the fourth generation⁸. None of these studies have explored the impact of these long-term low dietary fibre trends on gut bacteria production of short-chain fatty acids. This is a significant gap given that production of short-chain fatty acids by the gut bacteria influences colon cells development, lipids levels or appetite³.

Because short-chain fatty acids production is related to the amount of fibre intake, we believe that the current trends in lower fibre intake especially in younger generations

may have led to changes in the functionality of their gut bacteria. Specifically, we hypothesize that production of short-chain fatty acids is lower in younger generations compared to older generations and these dietary habits may also have affected the gut bacteria composition. To our knowledge, no research has been done to demonstrate that this hypothesis is valid or not. Therefore, we would like to test this hypothesis in a cross-over clinical trial where gut bacteria production of short-chain fatty acids, gut bacteria composition, metabolic profiles, glucose, insulin, lipid, gut hormones and inflammatory marker levels will be measured in duos or trios of participants (in direct link) who will take dietary fibre intervention daily for 4 weeks and compare these results with placebo intake over 4 weeks.

We want to investigate this hypothesis in women from 2 or 3 generations in direct link from the same family, such as grandmother, mother and daughter. At birth, mothers transmit gut bacteria to their offspring and therefore the maternal microbiome plays an important role in shaping the early composition of offspring's gut microbiota when compared to fathers. Mother's breast milk also influences the gut microbiome of their offspring in early life. However, there is little information on these maternal influences in the late life of offspring and especially in response to dietary fibre intake. Therefore, we want to determine if there is a transgenerational similarity in gut microbiome composition, metabolic profiles and clinical outcomes in response to 4-week high intake of dietary fibres compared to placebo. This approach (individuals in direct link and female participants across all generations) will allow us to 1) determine if there is a maternal influence on the gut microbiome and responses to dietary fibres of younger generations in late life and 2) have a less heterogenous cohort by focusing on women only which will allow for a better understanding of the data.

2. Study Hypothesis:

We hypothesize that compared to placebo, the dietary fibre intervention will lead to a higher production of short-chain fatty acids by the older generation's gut microbiota when compared to that of the younger generation which will translate into differential responses of gut microbiota composition, glucose, insulin, lipids, gut hormones and inflammatory markers levels.

3. Study Aim:

Investigate the effects of a dietary fibre blend taken over a 4-week period on the production of short-chain fatty acids by the gut microbiota, microbiota composition and health outcomes (glucose, insulin, lipids, gut hormones and inflammatory markers levels) of individuals from 2 or 3 generations in direct link (grandmother, mother and daughter).

4. Primary Outcome:

Comparison of the change in SCFA production from baseline to the end of the intervention between grandmothers, mothers and daughters between dietary fibre intervention and placebo.

5. Secondary Outcomes:

- Comparison of gut microbiota composition from baseline to the end of the intervention between grandmothers, mothers and daughters between dietary fibre intervention and placebo.
- Comparison of metabolic profiles of urine and stool samples from baseline to the end of intervention between grandmothers, mothers and daughters between dietary fibre intervention and placebo.
- Comparison of blood glucose levels from baseline to the end of intervention between grandmothers, mothers and daughters between dietary fibre intervention and placebo.
- Comparison of blood insulin levels from baseline to the end of intervention between grandmothers, mothers and daughters between dietary fibre intervention and placebo.
- Comparison of gut hormone levels from baseline to the end of intervention between grandmothers, mothers and daughters between dietary fibre intervention and placebo.
- Comparison of blood lipid levels from baseline to the end of intervention between grandmothers, mothers and daughters between dietary fibre intervention and placebo.
- Correlation of 3 days food diary information with gut bacteria production of SCFA among the 2 or 3 generations.

- Correlation of 3 days food diary information with gut bacteria composition among the 2 or 3 generations.
- Correlation of 3 days food diary information with urine metabolic profiles among the 2 or 3 generations.

6. Study methodology:

- Randomised, placebo controlled, double-blinded, cross-over study
- 4 weeks intervention (dietary fibre/placebo) 4 weeks wash-out 4 weeks intervention (opposite arm of intervention)

7. Intervention products:

The fibre intervention product will contain in equal proportions inulin, pectin and oat beta-glucan.

The placebo product will contain cellulose.

The intervention products will be sourced from Nestlé.

The fibre intervention and placebo products will be powders stored in sachets that will look identical and identically-packaged and participants will be able to add them to and mix them with their meals. The amount of intervention taken daily will be increased gradually (see below) to allow participants to adapt to the increased intake of dietary fibre and reduce the likelihood of gastrointestinal discomfort.

Both researchers and study participants will be blinded to the order in which the interventions will be given. The blinding process will be conducted by an independent researcher of the study team. This is done in order to avoid any bias when analysing the data. Unblinding of the study interventions will be done by the same researcher who was involved in the blinding process and it will be done at the end of the clinical study which is after the last study visit of the last participant.

Emergency unblinding will only be conducted in medical emergencies when the appropriate management of the participant necessitates knowledge of the treatment, or in the event that expedited reporting to the Research Ethics Committee (REC) of an unexpected and related Serious Adverse Event (SAE) is required. In the event that emergency unblinding of an individual participant is required, authorised members of the research team will follow trial procedures to unblind the participant in question and proceed with expedited reporting if required. Unblinding should only be considered if

management of the participant would differ depending on whether they were on placebo intervention (cellulose) or dietary fibre intervention (fibre mix of inulin, pectin and oat beta-glucan).

Randomization of study participants to the order in which they will receive the intervention products (placebo and dietary fibre) will be done by SealedEnvelope.com Participants will take the dietary supplements twice daily over 28 days in the order outlined below:

10g/day (5g morning or lunch and 5g dinner) from day 1 to day 4 20g/day (10g morning or lunch and 10g dinner) from day 5 to day 12 30g/day (15g morning or lunch and 15g dinner) from day 13 to day 28

After the wash-out period, the same procedure as above will be repeated but participants will consume the opposite arm of the intervention. For example, if in the first four weeks of the intervention period of the study, they consumed the placebo product, in the second four weeks of the intervention period of the study, they will consume the dietary fibre product.

Participants will be asked not to consume any intervention products on the study visit. At the end of study visits 1 and 3, participants will receive 56 sachets of intervention products. At study visits 2 and 4, participants will be asked to bring the empty sachets to assess compliance with the intervention. Throughout the 2 study intervention periods, participants will be asked to complete daily the Intervention Product Reminder sheet whenever they take the intervention product. This will also allow for assessing compliance with the intervention.

Intervention products will be stored in sachets and boxes in the Commonwealth Building of Hammersmith campus, Imperial College London.

8. Participants:

10 duos or trios (20-30 participants) females

Inclusion criteria:

- Any of the following groups of people (in direct descent and from the same family):
 - Grandmother, mother and daughter

- Mother and daughter
- Grandmother and granddaughter
- Age 18-85 (inclusive)
- BMI: 18.5-30 kg/m² (inclusive)
- Considering themselves healthy

Exclusion criteria:

- Intake of antibiotics in the past 3 months and during the study
- Intake of probiotic supplements in the past month and during the study
- Regular intake of laxatives in the past month and during the study
- Subjects with the following conditions:
 - Inflammatory Bowel Disease (IBD)
 - Irritable Bowel Syndrome (IBS)
 - Coeliac Disease
 - Type 12 Diabetes
 - Any type of cancer
 - Autoimmune conditions
 - Conditions that affect the liver
 - Conditions that affect the pancreas
- Subjects who require medical intervention in the coming 3 months
- Smokers
- Shift workers
- Gluten intolerance
- Pregnant and lactating women
- Subjects living in care homes
- had weight changes >5% in the preceding 3 months
- Subjects who are unable to give informed consent by themselves
- Subjects who are currently participating in other clinical trials

Support of number of volunteers:

This is a pilot exploratory study in a new area of research and therefore statistical power calculation is not possible.

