The collected samples (stool, urine and blood) will be analysed for: gut microbiota composition (from stools) through 16S rRNA sequencing and qPCR (quantitative Polymerase Chain Reaction); metabolites produced by the gut microbiota (from stools and urine) thorough NMR (Nuclear Magnetic Resonance), GC-MS (gas chromatography coupled with mass spectrometry), LC-MS (liquid chromatography coupled with mass spectrometry), LC-MS (liquid chromatography coupled with mass spectrometry), blood glucose, insulin, gut hormones (PYY and GLP-1), inflammatory markers (C reactive protein) and lipid levels.

11. Statistical Analysis

Statistical tests, such as ANOVA (Analysis of Variance) and t-tests (paired and unpaired) will be used to compare different groups: study participants groups, dietary fibre groups and placebo groups. Correlation analysis (Pearson and/or Spearman) and linear models will be used to analyse the relationship between gut bacteria taxa, short-chain fatty acids levels, metabolites levels, food diary information and demographics. Statistical significance levels will be p<0.05.

Various platforms will be used to analyse the data. Gut microbiome composition will be analysed using 16S rRNA sequencing on Illumina MiSeq and statistical analyses will be performed in R. Species diversity and richness will be calculated and statistical tests include t-tests and Mann-Whitney U tests, statistical significance p<0.05. Species diversity and richness and their changes from baseline between grandmother, mother and offspring will be compared. Data from placebo and dietary fibre intervention will be compared.

Short-chain fatty acids (SCFA) production from stool samples will be measured using GC-MS (Gas Chromatography coupled with Mass Spectrometry). T-tests (paired and/or unpaired) and ANOVA tests will be used to determine whether there are significant differences in SCFA production between grandmothers, mothers and offspring from baseline to end of intervention. Data from placebo and dietary fibre intervention will be compared. Significance levels will be p<0.05.

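### The Introduction says the direct-line cohort will determine maternal influence and transgenerational similarity, but no listed analysis tests whether relatives are more alike than non-relatives, and no comparator isolates a maternal effect

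*Combined protocol and SAP*

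**What the plan says.** Section 1 (Introduction) gives two reasons for the cohort that concern families. The investigators want to "determine if there is a transgenerational similarity in gut microbiome composition, metabolic profiles and clinical outcomes" in response to fibre compared with placebo, and they say that enrolling female relatives in direct line will let them "determine if there is a maternal influence on the gut microbiome and responses to dietary fibres of younger generations in late life".

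The rest of the plan is framed as differences between generations:

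- Section 2 (Study Hypothesis) expects "higher production of short-chain fatty acids by the older generation's gut microbiota when compared to that of the younger generation".
- Section 4 (Primary Outcome) is a "Comparison of the change in SCFA production from baseline to the end of the intervention between grandmothers, mothers and daughters", and between products.
- Section 5 (Secondary Outcomes) has six comparisons of the same form and three correlations of food-diary data with SCFA, microbiota composition and urine metabolic profiles.
- Section 11 (Statistical Analysis) names ANOVA, paired and unpaired t-tests and Mann-Whitney tests. For the microbiome, "Species diversity and richness and their changes from baseline between grandmother, mother and offspring will be compared". It also names Pearson or Spearman correlation and linear models among taxa, SCFA, metabolites, diet and demographics, and PCA to find chemicals that distinguish the generations. Similarity is mentioned once, for food diaries, and is assigned to ANOVA and t-tests.

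Section 8 (Participants) sets the size at "10 duos or trios (20-30 participants) females" and says that a "statistical power calculation is not possible". It admits trios, mother-daughter duos and grandmother-granddaughter duos.

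**The concern.** Resemblance between relatives is a statement about covariance within families. A comparison of generations is a statement about means. The two are separate: generations can differ clearly while each daughter closely resembles her own mother, and generations can have equal means while relatives are no more alike than strangers.

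If the plan is followed as written, the question that motivates recruiting relatives goes unanswered, although comparing generations would not by itself need relatives. The maternal part has a further difficulty. Even a convincing family resemblance could not be attributed to the mother without some contrast that separates maternal transmission from shared genes, household or diet.

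**Working it through.** **1. Match each listed analysis to the two claims.**

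| Listed analysis | What it compares | Relatives v. non-relatives? |
|---|---|---|
| t-tests, ANOVA, Mann-Whitney | Generations, or fibre v. placebo | No |
| Correlations, linear models | One variable with another | No |
| PCA | Chemicals that separate generations | No |
| ANOVA and t-tests on food diaries | Differences and similarities in diet | No |

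There is no mother-daughter correlation, intraclass correlation, family term, between-person microbiome distance or equivalence margin.

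**2. What the generation tests do when family resemblance varies.** The plan has no power figure to reproduce; only its size checks (10 × 2 = 20, 10 × 3 = 30). Simulation: 10 duos, normal data with SD 1, two-sided alpha 0.05 (the plan states 0.05 but not sidedness), 20,000 runs. The family correlation ρ is an assumed range, since the documents give none.

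| Paired t-test rejects | ρ = 0 | 0.3 | 0.5 | 0.8 |
|---|---|---|---|---|
| No generation difference | 4.8% | 5.1% | 4.8% | 5.1% |
| 1 SD generation difference | 51% | 67% | 80% | 99% |

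The first row does not move with ρ, so a non-significant result carries no information on resemblance. The second row shows that a clear generation difference can coexist with strong resemblance. With 10 complete trios and no generation difference, repeated-measures ANOVA on generation also rejects about 5% of the time at every ρ.

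**3. Non-significance is also weak evidence that means are equal.** With 10 pairs, 50% power for the paired t-test corresponds to 0.69 SD of the paired difference (noncentral t, 9 df). That SD is √(2(1 − ρ)) outcome SDs. In outcome SDs, the difference missed half the time is 0.69 × √2 = 0.98 at ρ = 0 and 0.69 × √0.4 = 0.44 at ρ = 0.8.

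**4. What a family-resemblance test could achieve.** Ten duos give 10 within-family older-younger pairs and 10 × 10 − 10 = 90 between-family pairs. The table gives illustrative power of a permutation test of within- versus between-family distance, assuming every feature has the same family correlation. Ranges are spreads between repeated simulations. Type I error was about 4-5%.

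| Features | ρ = 0.1 | 0.2 | 0.3 |
|---|---|---|---|
| 20, independent | 38% | 85% | 99% |
| 20, inter-correlated at 0.5 | 14% | 34-40% | 61-63% |
| 1 | 8-10% | 14% | 20% |

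**5. Single markers.** For a mother-daughter Pearson correlation with 10 duos, the critical |r| is 0.632. Power is 13%, 33% and 87% at ρ = 0.3, 0.5 and 0.8. An observed r of 0.5 has 95% limits tanh(0.549 ± 1.96/√7) = −0.19 to 0.86. With 10 complete trios, an F test of the family effect has power of 43%, 77% and 99% at the same three values.

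**6. Maternal attribution.** No paternal relative or unrelated household member is described. The grandmother-granddaughter criterion requires direct descent in the same family but does not state that the link runs through the mother.

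**The case against.** The strongest reply is that this is a pilot. The two claims sit in the Introduction, no endpoint states maternal influence or within-family similarity, and the hypothesis is a generation difference, which the listed tests do address. That limits the weight of the point: the primary analysis is not affected. Pilot status also explains the missing power calculation. It does not explain why the stated reason for the cohort has no analysis.

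Three stronger readings are tempting, and the documents do not support them.

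- *The plan tests only mean differences.* It does not. Correlations, linear models and PCA are also listed, but none is specified to compare relatives with non-relatives.
- *The generation tests ignore family links, so shuffling families would change nothing.* This is true of the mean difference and of an unpaired test. It is not true of a paired t-test if pairs are relatives: shuffling changes the standard error and the p-value, as the second row of the simulation implies.
- *The investigators will read non-significance as similarity.* Nothing in the documents says so. It is a risk while no other analysis bears on similarity.

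A fair objection also applies to the remedy. The favourable power figures need many nearly independent features that all share the same family correlation, and real taxa and metabolites are unlikely to meet that. Precision must therefore be stated with the result.

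**Conclusion.** The point stands as a mismatch between a stated purpose and the listed analyses. The data to be collected can support an exploratory look at family resemblance, because women from different families serve as unrelated pairs. They cannot, with the comparators described, establish maternal influence. A reader might infer from the eligibility wording that paternal-line duos will be enrolled; the documents do not say this, only that the criterion does not exclude them.

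The mismatch itself needs no numerical assumption. The power figures rest on normal data and assumed family correlations, and are illustrations rather than predictions. They support one firm statement: with 10 families, multivariate profiles may reveal moderate resemblance, single markers will reveal only strong resemblance, and a null result will not show its absence. It should be corrected, but it does not threaten the primary comparison.

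**What to change.** Add one exploratory analysis to section 11, at baseline and for the fibre-minus-placebo change:

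- **Profiles.** Use a permutation test of older-younger distances within versus between families (for example Bray-Curtis or Aitchison for taxa, Euclidean for metabolic profiles). Permute family labels within generation and within relationship type (mother-daughter, grandmother-granddaughter, trio). For the change, take account of treatment sequence, since section 7 randomises participants without mentioning family and relatives may receive different orders.
- **Single markers.** Report an intraclass correlation or mother-daughter correlation with its confidence interval, not a significance verdict.
- **Precision.** State in advance that 10 families give limited precision and that a null result will not be read as absence of resemblance.

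In section 1, replace the claim to determine maternal influence with *explore familial resemblance along the female line*. State in section 8 whether grandmother-granddaughter duos must be linked through the mother.

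The cost is one extra analysis, some rewording and a more modest stated conclusion. No new visits, samples or participants are needed. Restricting permutations to relationship type reduces the number available: an assumed split of 4, 3 and 3 families gives 4! × 3! × 3! = 864 rearrangements of one generation's labels, against 10! = 3,628,800 unrestricted. The family mix should therefore be reported with the result.

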Afterwards, they will have a blood test to check they are not anaemic or diabetic and height and weight measurements will also be taken. They will also have an electrocardiogram (ECG) and blood pressure will be recordedtaken. All women of childbearing age will have a pregnancy test. Participants will also be asked to complete, together with the researcher taking consent, a brief questionnaire assessing their eligibility for the study. Specifically, their weight, height, blood pressure, the result of the pregnancy test will be recorded, as well as any information related to family history of disease, or any medication they are currently taking. In addition, personal information, such as their address (for the collection kits to be sent over), GP details, next of kin will be recorded.

They will also be explained how to use the urine and stool collection kits. Fasted urine and stool samples will be collected by study participants on the day when they come for each study visit. If the results of the blood test will make participants eligible for the study, they will be sent by post the urine and stool collection kits which they will use to bring their samples in on the first study visit. If the blood tests results indicate that they are not eligible for the study, participants will be informed (either by phone or e-mail) by a member of the research team that they will not be able to participate in the study because they do not fit the eligibility criteria.

During the health screening visit, participants will also be explained how to complete the 3 days food diary. If the results of the blood test will make participants eligible for the study, they will be sent by post the first 3 days food diary which they will bring filled in with what they ate and drank 3 days before the first study visit. Eligible participants (once the blood tests results will come and indicate that participants are eligible to participate) will also be sent by post a questionnaire related to demography and dietary habits.

Participants will be advised not to start any strenuous physical activities or go on new diets as these may lead to conflicting results. They will also be asked to consume a similar evening meal the day before each study visit (to ensure consistency between study visits), avoid alcohol the day before each study visit and fast overnight (for 12h) before each study visit (drinking water will be fine).

Visits 1, 2, 3 and 4– Study Visits

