There is a 4-week gap (28 days +/-4 days) between Study Visits 1 and 2, followed by a 4-week wash-out period (28 days +/-7 days) and then followed by Study Visits 3 and 4 (4-week gap 28 days +/-4 days between Study Visits 3 and 4) (Figure 1).

[figure not shown]

Figure 1. Diagram of study visits; V=study visit

Participants will come fasted at the Study Visits and they will not have consumed any intervention products in the morning. They will bring their stool and urine samples, the 3 days food diaries and the participants questionnaire. They will also undergo a physical examination (body weight, height and fat percentage) and have their blood pressure measured and recorded. Women of childbearing age will have a pregnancy test at the beginning of each study visit. If the pregnancy test result is positive, they will be withdrawn from the study. No more data and samples will be collected from them. All the data and samples that were collected up to their withdrawal will be used in data analysis.

At Study Visits 2 and 4 participants will be asked to complete a Visual Analogue Questionnaire where they will rate how the dietary intervention has affected various gastrointestinal symptoms, such as constipation, bloating, appetite.

At 09:30 an intravenous cannula will be inserted into one arm for blood sampling by an adequately trained doctor, nurse or member of research team under aseptic conditions. Just before 10:00 fasting blood samples will be taken through an intravenous peripheral cannula (-15min and -5min). Participants will then receive a standardised breakfast at 10:00.

Postprandial blood samples will be taken at 15, 30, 45, 60, 90, 120 180 and 240 minutes after having the standardised breakfast to measure gut hormones, lipids, glucose, and insulin and inflammatory marker levels. 10ml of blood samples will be

taken at each sampling point, and therefore 100ml (10 x 10ml) during each study visit will be taken (Figure 2).

[figure not shown]

Figure 2. Diagram of Study Visit protocol; VAS=Visual Analogue Scale

Appetite and wellbeing will be assessed at the following timepoints (Figure 2): -15, 0, 30, 60, 120,180 and 240 minutes using a visual analogue scale (VAS).

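### Section 11 plans no baseline covariate for the primary change-in-SCFA comparison; if baseline is each period's own visit, adjusting for it would be more precise than subtracting it, at little cost

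*Combined protocol and SAP*

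**What the plan says.** Section 4 defines the primary outcome as a "Comparison of the change in SCFA production from baseline to the end of the intervention between grandmothers, mothers and daughters between dietary fibre intervention" versus placebo. For this outcome Section 11 says "T-tests (paired and/or unpaired) and ANOVA tests will be used to determine whether there are significant differences in SCFA production" between the generations, and then only that "Data from placebo and dietary fibre intervention will be compared". It names no baseline SCFA covariate and no period term. Regression appears once in Section 11, for a different purpose: "linear models will be used to analyse the relationship between gut bacteria taxa, short-chain fatty acids levels, metabolites levels, food diary information and demographics".

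No section says which visit is the baseline. Section 9 states "Fasted urine and stool samples will be collected by study participants on the day when they come for each study visit", and it places Visits 1 and 2 around the first intervention period, "followed by a 4-week wash-out period (28 days +/-7 days) and then followed by Study Visits 3 and 4". A stool sample will therefore exist at the start and the end of each period. Change from baseline is also planned for a secondary outcome: "Species diversity and richness and their changes from baseline between grandmother, mother and offspring will be compared".

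**The concern.** In a cross-over each woman is her own control. Her stable SCFA level drops out as soon as her end-of-fibre value is compared with her end-of-placebo value. If a separate baseline is also subtracted in each period, there is no stable level left to remove, and two more single-sample measurements enter the estimate with full weight. As a covariate, the baseline difference enters only with the weight that its correlation with the outcome supports.

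What is at stake is interval width. Section 8 allows 20 to 30 women in 10 families, so at most 10 per generation and fewer where families are duos. In a pilot of that size, precision decides what can be learned, and the samples needed are already collected.

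**Working it through.** The protocol gives no power calculation, SD or correlation (Section 8 says power cannot be calculated), so there is no figure to reproduce.

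**Inputs from the protocol.** 20 to 30 women in 10 duos or trios (Section 8); two periods with stool at Visits 1 to 4, nominally 28 days apart (Section 9); significance at p<0.05 (Section 11; two-sided assumed). All correlations below are assumptions.

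**Step 1: which baseline.** If Visit 1 is the only baseline, (end fibre − V1) − (end placebo − V1) = end fibre − end placebo. It cancels, and the point does not arise. The rest takes Visit 1 for period 1 and Visit 3 for period 2.

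**Step 2: variances.** For each woman let D = end-of-fibre minus end-of-placebo value, and B = fibre-period baseline minus placebo-period baseline.
- Raw change analyses D − B: variance = var(D) + var(B) − 2cov(D,B).
- Adjustment regresses D on B: variance = var(D) − cov(D,B)²/var(B).
- With b = corr(D,B) and k = SD(B)/SD(D), raw/adjusted = (1 + k² − 2kb)/(1 − b²) = 1 + (k − b)²/(1 − b²). Before the cost of estimating the slope, this is never below 1.
- With equal SDs (k = 1) it is 2/(1+b): 2.0 at b = 0, 1.67 at 0.2, 1.33 at 0.5.

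**Step 3: plausible b.** Take a stable level plus a fluctuation with 4-week autocorrelation phi. With equal spacing, b = (phi − phi³)/(2(1 − phi²)) = phi/2, so the ratio is 4/(2+phi). That gives 4/2.2 = 1.82, 4/2.5 = 1.60 and 4/2.8 = 1.43 at phi = 0.2, 0.5 and 0.8.

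**Step 4: small samples.** 20,000 simulated trials per setting, stable share 0.4 of the variance, balanced sequences, period effect 0.3 SD, a sequence term in both models, family correlation not modelled. Type I error was 0.047 to 0.055 for both methods. Each cell gives raw change, then adjusted; power is for 0.5 SD.

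| phi | Variance ratio, n=20 | Half-width n=20 (SD) | Half-width n=30 (SD) | Power n=20 | Generation contrast 10 v 10: half-width (SD) | Its power |
|---|---|---|---|---|---|---|
| 0.2 | 1.74 | 0.67, 0.51 | 0.53, 0.40 | 32%, 49% | 1.34, 1.03 | 12%, 16% |
| 0.5 | 1.50 | 0.54, 0.44 | 0.43, 0.35 | 44%, 60% | 1.08, 0.89 | 15%, 20% |
| 0.8 | 1.35 | 0.33, 0.29 | 0.27, 0.23 | 84%, 93% | 0.67, 0.58 | 31%, 40% |

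**Step 5: where the gain shrinks.**
- If women respond differently to fibre, so that SD(D) is 25% above SD(B) (k = 0.8), the ratio is 1 + 0.64 = 1.64 at b = 0, 1 + 0.36/0.96 = 1.38 at b = 0.2, and 1 + 0.09/0.75 = 1.12 at b = 0.5.
- If correlation within a period far exceeds correlation across periods, b is large. With 20 women, the adjusted/raw CI width ratio was 0.94 for correlations 0.8 within and 0.4 across, 1.00 for 0.9 and 0.3, and 1.02 for 0.95 and 0.3.
- With b = 0.75 and 6 v 6 women there is no gain (variance ratio 0.98).

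**Step 6: cost of the covariate.** The variance penalty is about f = (1 + 1/(df − 2)) × (t(df−1)/t(df))², and with k = 1 break-even is b = 2/f − 1.

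| Analysis | df | f | Break-even b |
|---|---|---|---|
| 30 women | 26 | 1.05 | 0.91 |
| 20 women | 17 | 1.08 | 0.86 |
| 10 duos, family blocks | 8 | 1.23 | 0.63 |

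**The case against.** The strongest reply is that nothing in the plan is wrong. Change from baseline is a valid endpoint, the study is an exploratory pilot with no power target, and Section 11 presents its tests as examples. That stands: this is an improvement, not the correction of an error.

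The point is also doubly conditional. It needs the per-period reading of baseline, and its size rests on assumed correlations. Both limits stand. Equal 4-week spacing does make the settings with no gain, where within-period correlation is far above across-period correlation, the less likely ones.

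The larger power gains are for the overall fibre effect, whereas the primary outcome compares generations. There, power for 0.5 SD stays low either way, and 10 v 10 is the best case. The interval still narrows. The simulated raw-change model also contains a sequence term, so it is not strictly the planned t-test.

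Family blocking raises the cost: 23% of variance with 10 duos. Under equal or decaying visit correlations, the adjusted interval was still narrower in that setting (width ratios 0.78 to 0.91). With within-period correlation of 0.8 to 0.95 the ratios were 1.00 to 1.08.

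Neither estimator wins under every form of carry-over. Suppose a fraction L of the fibre effect remains at Visit 3, with k = 1. If it is gone by Visit 4, raw change overstates the effect by L/2 and the adjusted estimate by bL/2; at L = 0.2 and b = 0.2 these are 10% and 2%. If it persists equally to Visit 4, raw change is unbiased and the adjusted estimate understates by (1 − b)L/2 = 0.8 × 0.1 = 8%. The no-carry-over assumption must therefore be stated.

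Two further objections do not count against the change. The model needs all four visits from each woman, but so does a paired test of change scores. Section 4 does not say whether SCFA means the total or individual acids, but the model can be run on whichever value is analysed.

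**Conclusion.** The point holds. Section 11 plans no baseline covariate for the primary comparison. On the per-period reading of baseline, raw change is less precise than adjustment over the plausible range of correlations. With equal SDs and a stable level plus decaying fluctuation, its variance is 1.33 to 2.0 times the adjusted variance before the covariate's cost, and 1.35 to 1.74 times in the simulations with 20 women. This is a loss of precision, not bias.

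The size is uncertain because the documents give no correlations. The advantage is smaller if responses to fibre vary between women. It can vanish at high b (about 0.86 with 20 women, 0.63 with 10 duos in family blocks) or in very small generation groups. The change is worth making, but it does not rescue the power of the generation contrast.

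**What to change.** In Section 11:

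- Define baseline as Visit 1 for period 1 and Visit 3 for period 2.
- Analyse each woman's fibre-minus-placebo difference in end-of-period SCFA (Visits 2 and 4) in a linear model with a sequence term, which carries the period effect, and the difference between her two period baselines as a covariate. Read the fibre effect at a baseline difference of zero, and compare generations on the adjusted difference.
- Use the within-woman baseline difference, not the raw baseline level. Generations are not randomised. With generations 1 SD apart at baseline and no true difference in change, adjusting a single period's change for raw baseline shifted the contrast by about 0.5 SD at a baseline-to-end correlation of 0.5, and about 0.3 SD at 0.7.
- State that interpretation assumes no carry-over into Visit 3, and report unadjusted change as a sensitivity analysis.
- Apply the same model to species diversity and richness. Apply it to glucose, insulin, lipids and gut hormones only once a single summary of the ten blood samples per visit is defined.

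Section 4 can keep change as the outcome, because adjusting the change for the same covariate gives the identical treatment estimate: (D − B) regressed on B differs from D regressed on B only in the slope. The cost is Section 11 wording and one degree of freedom, with no new samples or visits.
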